#### Europe:

- 1. Response at a single dose of 600 mg (1043 mg cumulative) of peanut protein: The proportion of subjects ages 4-17 who tolerate a single dose of 600 mg of peanut protein with no more than mild symptoms at the Exit DBPCFC
- 2. Response at a single dose of 300 mg (443 mg cumulative) of peanut protein: The proportion of subjects ages 4-17 who tolerate a single dose of 300 mg of peanut protein with no more than mild symptoms at the Exit DBPCFC
- 3. The maximum severity of symptoms in subjects ages 4-17 occurring at any challenge dose of peanut protein during the Exit DBPCFC
- 4. Response at a single dose of 1000 mg (2043 mg cumulative) of peanut protein: The proportion of subjects ages 18-55 who tolerate a single dose of 1000 mg of peanut protein with no more than mild symptoms at the Exit DBPCFC

Each comparison will be evaluated for statistical significance (two-sided p<0.05) only if all of the preceding tests in the hierarchy and the primary analysis of the primary endpoint are statistically significant in favor of AR101. Similar to the primary efficacy analysis of the primary endpoint, the ITT Population will be used as the primary population in pediatric subjects for analysis of key secondary endpoints as part of the hierarchical testing procedure. This closed testing procedure maintains the overall Type I error rate at 0.05 (EMEA CPMP, 2002; Cook et al., 2008). If any of the preceding tests are not significant, the p-value will be displayed for informational purposes only.

#### 9.3.1. Desensitization Response Rates

The number and percent of subjects with a desensitization response will be reported by treatment group within pediatric subjects. The desensitization response rate and its 95% confidence interval will be calculated for each treatment group with Wilson (score) confidence limits for the binomial proportion. The 95% confidence interval for the treatment difference (AR101 desensitization rate minus placebo desensitization rate) will be based on Farrington-Manning CI for the difference in binomial proportions.

The analysis will test for the difference in response rates (AR101 minus Placebo) in the ITT Population. The Farrington-Manning test will be used to test for a non-zero treatment effect at the two-sided 0.05 significance level. AR101 is considered to have met this key secondary efficacy endpoint if the lower bound of the corresponding test-based 95% confidence interval is greater than 0.

This corresponds to the following hypotheses:

- H0: Proportion of active subjects with a desensitization response ≤ proportion of placebo subjects with a desensitization response
- HA: Proportion of active subjects with a desensitization response > proportion of placebo subjects with a desensitization response

#### 9.3.2. Maximum Severity of Symptoms

The objective of analyzing this key secondary efficacy endpoint is to determine if pediatric subjects from the AR101 group will have less chance of developing more severe levels of symptom severity compared to pediatric subjects from the placebo group. Symptom severity will be determined at 4 levels: 0-None, 1-Mild, 2-Moderate, 3-Severe or higher (severe, life threatening, fatal). Subjects who experience no symptoms will be assigned a severity of 0-None. Symptom severity data will be collected at each challenge dose of peanut protein during the Exit DBPCFC (3 mg, 10 mg, 30 mg, 100 mg, 300 mg, 600 mg, and 1000 mg). The analysis of this key secondary endpoint will be conducted in the pediatric subject subset of the ITT population.

The maximum severity of symptoms observed in the DBPCFC at any dose (1000 mg or lower) will be used for each subject in the primary analysis of this key secondary endpoint.

The number and percent of subjects by maximum severity at the Exit DBPCFC will be tabulated by treatment arm. The Cochran-Mantel-Haenszel statistic (with equally spaced scores) will be used to test for a treatment difference. The test will be stratified by Region. The mean of the numerical values assigned to maximum severity by treatment group will also be reported.

The primary analysis of this key secondary endpoint will test the following hypotheses:

- H0: The maximum severity of symptoms at the Exit DBPCFC at any dose is the same for the AR101 and placebo treatment arms in all strata.
- HA: The maximum severity of symptoms at the Exit DBPCFC at any dose is different between the AR101 and placebo treatment arms in at least one stratum.

For the primary analysis of this key secondary endpoint, subjects without an Exit DBPCFC will be assigned their maximum severity during the Screening DBPCFC, which equates to no change from screening.

#### 9.4. ADDITIONAL ANALYSIS OF KEY SECONDARY ENDPOINTS

Analysis of the key secondary endpoints will be repeated in the pediatric subset of the Completer population as a sensitivity analysis and also in the PP population (if sufficiently different from the Completer population; section 4.7). Additionally, subjects with an indeterminate Exit DBPCFC will be excluded as a sensitivity analysis of the key secondary efficacy endpoints in the ITT subset.

Analysis of the key secondary efficacy endpoints will be repeated in the following subgroups in the ITT and Completer populations as supportive analyses:

- By Region (NA and EU)
- By Pediatric Age group (Children 4-11 and Adolescents 12-17)
- By Region and Pediatric Age group (NA Children, NA Adolescents, EU Children, and EU Adolescents)

For countries with at least 3 subjects in each treatment arm, subgroup analyses may be performed by country.

A sensitivity analysis will be conducted on the common risk difference of the desensitization response rates similar to the sensitivity analysis of the primary efficacy endpoint (Section 9.2). This sensitivity analysis will be performed in the ITT and Completer populations.

As supportive analyses, the analysis of maximum severity of symptoms during the Exit DBPCFC will be repeated for the maximum severity observed in the DBPCFC at any dose up to a maximum challenge of 600 mg. The analysis will be repeated up through a maximum challenge of 300 mg, 100 mg, 30 mg, 10 mg, and 3 mg. Together with the primary analysis of this key secondary endpoint in the ITT population of pediatric subjects, this family of tests will be conducted hierarchically to maintain a familywise Type I error rate of 5%. Each test within this family will be conducted at the 5% level if the preceding test was significant at the 5% level; starting with the primary analysis of this key secondary endpoint (maximum severity at any dose up through and including 1000 mg) and followed by each lower level (600 mg, 300 mg, 100 mg, 30 mg, 10 mg, and 3 mg), until a test is not significant at the 5% level. Analytical methods described in Section 9.3.2 will be used for these analyses.

A sensitivity analysis for the maximum severity of symptoms in the ITT population of pediatric subjects using multiple imputation (MI) methodology may be explored to assess the impact of missing symptom severity data. We assume subjects with a missing exit DBPCFC tend to have more severe symptoms than Completers and thus are missing not at random (MNAR). The data to be used for the MI sampling will be chosen from subjects in the placebo group in sequential order of severity starting with the most severe symptoms. The percentage of placebo subjects with non-missing data to be used in the MI sample will be based on the percentage of AR101 subjects with missing data at the Exit DBPCFC. However, no fewer than 15 and no more than 30 placebo subjects with non-missing data will be used for the MI sample. The number of imputations will be set to the percentage of subjects across both treatment groups with missing data at the Exit DBPCFC but no fewer than 20 imputations will be used. For example, if 25% of AR101 subjects have missing Exit DBPCFC, then the worst 25% of observed Exit DBPCFC responses from the Placebo group will be used as the MI sample for missing AR101 and Placebo responses and a total of 25 imputations would be used.

These additional analyses will not be considered as part of the hierarchical testing procedure.

Subgroup analyses based on region will employ similar analytical methods as the nonsubgroup analyses with the exception of not including region as a factor in the model or as a stratification factor.

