4 SELECTION AND WITHDRAWAL OF SUBJECTS

4.1 Inclusion Criteria

Subjects who meet all of the following criteria are eligible for enrollment as study subjects:

- 1. Age 4 through 55 years (inclusive)
- 2. Clinical history of allergy to peanuts or peanut-containing foods
- 3. Serum IgE to peanut of $\geq 0.35 \text{ kU}_{\text{A}}/\text{L}$ [determined by UniCAPTM within the past 12 months] and/or a SPT to peanut $\geq 3 \text{ mm}$ compared to control
- 4. Experience dose-limiting symptoms at or before the 100 mg challenge dose of peanut protein (measured as 200 mg of peanut flour) on Screening DBPCFC conducted in accordance with PRACTALL (Practical Issues in Allergology, Joint United States/European Union Initiative) guidelines
- 5. Written informed consent from adult subjects
- 6. Written informed consent from parent/guardian for minor subjects
- 7. Written assent from minor subjects as appropriate (eg, above the age of 7 years or the applicable age per local regulatory requirements)
- 8. Use of effective birth control by female subjects of child-bearing potential
- 9. Not be residing at the same address as another subject in this or any peanut OIT study

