#### 2.3. BRIEF DESCRIPTION OF STUDY DESIGN

This is an international, multicenter, randomized, double-blind, placebo-controlled study of the efficacy and safety of AR101 in a characterized desensitization OIT regimen in peanutallergic individuals. The study will consist of a screening phase, that includes a Screening double-blind, placebo-controlled food challenge (DBPCFC), and a double-blind OIT Treatment Phase that includes an initial escalation period, an up-dosing period, and a maintenance period, followed by an Exit DBPCFC. The DBPCFC at screening and at exit is to be performed under double-blind conditions so that neither the subject, nor the subject's caregiver, nor any of the clinic staff (save for the unblinded preparer of the challenge foods) knows which challenge contains the peanut or the placebo. See SAP section 2.7 for a summary and protocol section 6.6 for additional details of the DBPCFC.

Peanut-allergic children and adults (ages 4-55 inclusive) will have an initial screening DBPCFC of up to 100 mg (144 mg cumulative) peanut protein or placebo. Those experiencing dose-limiting symptoms at or before the 100 mg dose of peanut protein (measured as 200 mg of peanut flour) will be eligible. Those who develop dose limiting symptoms (DLSs) in reaction to the placebo part of the screening DBPCFC will not be eligible. See Protocol Section 4 for a complete list of inclusion and exclusion criteria.

Approximately 500 peanut-allergic subjects will be randomized 3:1 to peanut OIT versus placebo. At least 80% of the subjects randomized will be children. All eligible subjects will receive escalating doses of either AR101 or placebo. The Treatment Phase comprises 3 periods:

- **Initial Escalation Period** 2 days in duration;
- Up-dosing Period This is defined as the time from the subject's first home dose of study product at 3 mg to the subject's first in-clinic dose at 300 mg, ideally 20

weeks in duration, but may be extended to a maximum of 40 weeks to accommodate dose reductions and re-escalations, if necessary;

• **Maintenance Period** – The Maintenance Period starts with the first home dose of 300 mg. Ideally, it will be 24 weeks in duration, but it may be extended by up to an additional 4 weeks (for a maximum Maintenance Period duration of 28 weeks), or to a total Treatment Phase duration of 68 weeks, whichever occurs first, to accommodate dose reductions and re-escalations that may occur during the final weeks of the Maintenance Period.

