#### 6.4. SIGNIFICANCE LEVEL

Unless stated otherwise, all statistical tests will be two-sided, with a significance level of 0.05. Confidence intervals (CIs) will be calculated at the 95% level, reflecting a type I error rate of 0.05.

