For the primary and key secondary endpoints involving desensitization rates, if a subject discontinues prior to the exit DBPCFC, they will be considered non-responders. Other sensitivity analyses involving alternative methods for handling subjects with missing exit DBPCFC are described in section 9.2.

For the key secondary endpoint of maximum severity of symptoms, if a subject discontinues prior to the exit DBPCFC, the maximum severity of symptoms during the exit DBPCFC will be imputed using the maximum severity of symptoms during the screening DBPCFC.

No imputations will be made for other missing data, unless specified otherwise.

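### SAP 9.4: at the 30, 10 and 3 mg caps, the severity tests impute a missing Exit challenge from Screening doses above the cap, which biases them against AR101 if its dropout is higher

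*SAP*

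**What the plan says.** The key secondary endpoint is the worst symptom severity (0 to 3) at any Exit dose. SAP 9.3.2 states: "The Cochran-Mantel-Haenszel statistic (with equally spaced scores) will be used to test for a treatment difference". SAP 9.4 adds versions capped at 600 mg and below: "The analysis will be repeated up through a maximum challenge of 300 mg, 100 mg, 30 mg, 10 mg, and 3 mg". It orders them as a step-down family with a claimed 5% familywise error rate and says: "Analytical methods described in Section 9.3.2 will be used for these analyses".

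For missing Exit challenges, SAP 9.3.2 says that "subjects without an Exit DBPCFC will be assigned their maximum severity during the Screening DBPCFC, which equates to no change from screening". SAP 7.6 gives the same rule for the endpoint: "the maximum severity of symptoms during the exit DBPCFC will be imputed using the maximum severity of symptoms during the screening DBPCFC". Neither limits the Screening value to a dose range, and no other section gives a rule for the capped versions.

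Two design facts matter. SAP 2.3 describes an "initial screening DBPCFC of up to 100 mg (144 mg cumulative) peanut protein or placebo", and Protocol 4.1 requires that subjects "Experience dose-limiting symptoms at or before the 100 mg challenge dose of peanut protein".

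**The concern.** At a cap below 100 mg, the imputed value can come from a dose outside the range being tested. Take a child with no symptoms through 30 mg and a moderate reaction at 100 mg at Screening, who then leaves before Exit. The literal rule scores that child as moderate through 3 mg, although the Screening severity through 3 mg was none. The stated rationale, no change from Screening, does not hold for that version.

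Because entry required a dose-limiting reaction by 100 mg, nearly every missing child is scored as symptomatic at every cap. In ARC001 (Protocol 1.2.2.1), 6 of 29 AR101 subjects left before the Exit challenge, while all 26 placebo subjects completed. AR101 completers had no moderate symptoms below 600 mg. If ARC003 behaves similarly, much of the AR101 severity at the lowest caps would be imputed from higher doses, and a real low-dose benefit could be hidden.

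**Working it through.** The documents state no figure for the capped tests, so there is none to reproduce. The severity distributions and reaction shares below are assumptions. Two different sets were used to show the range.

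**Test.** Mean-score form of the CMH test, scores 0 to 3, one stratum (region ignored), on expected proportions:

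z = (m_A − m_P) / √[S²(1/n_A + 1/n_P)], where S² is the variance of the scores over both arms (divisor N − 1). Negative z favours AR101.

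**Set 1: thresholds from Protocol 1.1**
- n = 374 and 125 (499 children in SAP 2.4, 3:1).
- Missing: 6/29 = 20.7% on AR101; 0% or 7% on placebo (assumed).
- Share reacting by dose d: 5% at 1 mg, 25% at 15 mg and 50% at 125 mg (middle of the Protocol's 100 to 150 mg), log-linear between points, divided by the share at 100 mg because all subjects reacted by then.
- Severity given a reaction: 30/60/10% mild/moderate/severe, so the mean score is 0.3 + 1.2 + 0.3 = 1.8. AR101 completers are symptom-free at these caps.
- Placebo thresholds at Exit: unchanged, or raised 2.19-fold (the ARC001 placebo change).

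Example at 3 mg, placebo shifted, none missing:
- F(100) = 0.25 + 0.25·ln(100/15)/ln(125/15) = 0.474.
- F(3) = 0.05 + 0.20·ln 3/ln 15 = 0.131, so 0.131/0.474 = 27.7% react by 3 mg at Screening.
- F(3/2.19) = 0.073, so 0.073/0.474 = 15.5% of placebo react by 3 mg at Exit.
- As written: m_A = 0.207 × 1.8 = 0.372; m_P = 0.155 × 1.8 = 0.278; S² = 0.577. z = 0.094/√(0.577 × 0.01067) = +1.2, p = 0.23.
- Dose-matched: m_A = 0.207 × 0.277 × 1.8 = 0.103, z = −3.2, p = 0.001.

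| 3 mg scenario | Symptomatic as written, AR101 vs placebo | z (p) | Symptomatic dose-matched | z |
|---|---|---|---|---|
| No shift, placebo missing 0% | 20.7% vs 27.7% | −1.5 (0.13) | 5.7% vs 27.7% | −6.3 |
| No shift, 7% | 20.7% vs 32.7% | −2.6 (0.01) | 5.7% vs 27.7% | −6.3 |
| Shift 2.19, 0% | 20.7% vs 15.5% | +1.2 (0.23) | 5.7% vs 15.5% | −3.2 |
| Shift 2.19, 7% | 20.7% vs 21.4% | −0.2 (0.88) | 5.7% vs 16.3% | −3.5 |

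Over the same four scenarios, as-written z is −2.9 to −5.9 at 10 mg (dose-matched −6.1 to −8.5) and −6.1 to −9.7 at 30 mg (dose-matched −7.8 to −11.1). With the 50% point at 100 or 150 mg instead, the as-written 3 mg p with 7% placebo missing spans 0.006 to 0.99, and the weakest 10 mg z is −2.5.

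**Set 2: assumed severities**
- n = 371 and 124 (495 children in Protocol 9.4).
- Share reacting at Screening by 3, 10, 30, 100 mg: 8, 25, 55, 100%. Screening maximum from all mild to all moderate.
- Completers' Exit severity, none/mild/moderate/severe, AR101 vs placebo: 97/3/0/0 vs 90/6/4/0% at 3 mg; 94/6/0/0 vs 80/10/9/1% at 10 mg; 90/10/0/0 vs 60/15/22/3% at 30 mg.

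At 3 mg with 20.7% vs 0% missing and all mild: m_A = 0.793 × 0.03 + 0.207 × 1 = 0.231; m_P = 0.06 + 0.08 = 0.14; S² = 0.185; z = 0.091/√(0.185 × 0.01076) = +2.0, p = 0.04.

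| Cap | Missing, AR101 vs placebo | z as written | z dose-matched |
|---|---|---|---|
| 3 mg | 20.7% vs 0% | +2.0 to +3.8 | −3.4 to −2.3 |
| 3 mg | 20.7% vs 5% | +1.1 to +2.6 | −3.3 to −2.4 |
| 3 mg | 20.7% vs 10% | +0.1 to +1.4 | −3.2 to −2.4 |
| 3 mg | 15% vs 5% | −0.2 to +1.3 | −3.4 to −2.7 |
| 3 mg | 10% vs 10% | −2.5 to −1.5 | −3.5 to −3.1 |
| 10 mg | 20.7% vs 0% | −1.1 to +1.9 | −4.7 to −2.8 |
| 30 mg | 20.7% vs 0% | −6.1 to −2.1 | −7.7 to −4.8 |

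At 100 mg the two rules coincide, because Screening also stops there.

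**No observed difference.** With 93/5/2% none/mild/moderate at 3 mg among completers of both arms, unequal dropout alone gives p < 0.0001 (20.7% vs 0%), 0.0002 to 0.003 (20.7% vs 5%) and 0.01 to 0.05 (15% vs 5%), all against AR101.

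**The case against.** The imputation sentence in SAP 9.3.2 opens by limiting itself to the primary analysis of the endpoint, and SAP 7.6 ends by ruling out other imputations unless specified. The authors may have meant a dose-matched value, or none, for the capped versions. That leaves intent open. But SAP 9.4 imports the 9.3.2 methods without exception, the SAP 7.6 rule for this endpoint carries no primary-analysis limit, and a programmer following the text would use the uncapped value.

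The analyses are labelled supportive, and SAP 9.4 places them outside the main hierarchy. The key secondary analyses are repeated in Completers, and SAP 10.5 tabulates severity by individual dose with no carry-forward stated. All of this stands and limits the consequence.

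Dose-matching also has a cost. A child who stopped because of reactions to low doses of study product, but first reacted at 30 or 100 mg at Screening, would be scored none at 3 mg. SAP 9.4's own multiple-imputation analysis assumes that missing subjects fare worse than Completers. The uncapped rule can therefore be defended as conservative, though not as no change from Screening.

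On direction, SAP 6.4 says "all statistical tests will be two-sided, with a significance level of 0.05" and the 9.4 step-down asks only for significance, whereas SAP 9.3 requires a result in favour of AR101. A reader might infer that an adverse artefact could open the next step. Neither set of assumptions gives a significant adverse result above 3 mg, and 3 mg is the last step, so this is a wording gap without a demonstrated consequence.

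**Conclusion.** The point holds on the literal text: for the 30, 10 and 3 mg caps the rule can import reactions from doses above the cap. The direction of the bias depends on dropout being higher on AR101; with equal 10% dropout the 3 mg result is only diluted. The size depends on thresholds and severities that the documents do not give. Across the two sets, the 3 mg test can lose significance or change sign. The reversal is not significant under the first set (p about 0.23) and is significant under the second when placebo dropout is 0%. The 10 mg test is weakened but still favours AR101 under the first set, and can be lost under the second. The 30 mg test is diluted only.

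A reader might infer that the low-dose results as a group measure dropout instead of reactions. The 30 mg results contradict that, and so do the 10 mg results under the thresholds taken from the Protocol. A reader might also infer a risk of a false efficacy claim or damage to the key secondary test. The bias runs against AR101, and that test is not capped below 100 mg. This is a modest correction, worth making before database lock.

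**What to change.** In SAP 9.4, with a matching line in 7.6:

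1. For each version capped at dose D, assign subjects without an Exit challenge their maximum Screening severity at doses up to D. For D of 100 mg or more this is the full Screening maximum, as now.
2. State that the Completer repeat covers each cap.
3. Count a step as significant only if it favours AR101, as SAP 9.3 already does.
4. Keep the uncapped rule as a sensitivity analysis, because dose-matching is less conservative at low caps for subjects who stopped after reacting to low doses of study product.

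The cost is a few sentences and a small programming change. Screening severity is already recorded at each dose, and the key secondary analysis does not change. The capped tests appear only in the SAP, so the Protocol needs no amendment. The rule should be set before unblinding, since choosing it afterwards would be open to challenge.

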# 9.5. ANALYSIS OF OTHER SECONDARY ENDPOINTS

If the primary efficacy analysis of the primary endpoint and all of the hierarchical testing of key efficacy secondary endpoints in pediatric subjects as described in Section 9.3 are found to be statistically significant, then statistical testing of the other secondary efficacy endpoints will continue in the order that they are listed in Section 3.2.2 according to the same hierarchical closed testing procedure used for the key efficacy secondary endpoints.

The ITT population of pediatric subjects will similarly be used for the hierarchical testing of the other secondary endpoints.

The other secondary endpoints are included in the overall hierarchical testing procedure. However, these endpoints are considered supportive in nature to the primary and key secondary endpoints. As such, no labeling claims will be made based on these endpoints if statistical significance is achieved, regardless of the success of the variables above them in the hierarchy.

Analysis of other secondary endpoints, as described below, will be performed on the pediatric subject subset (Ages 4-17) of the ITT and Completer populations. Analysis in the Completer population will not be considered for the hierarchical testing procedure.

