The key secondary endpoints will be tested in the ITT population in the hierarchical order specified in Section 3.7.1. If the primary efficacy analysis is significant at the 0.05 level, then the proportion of subjects who tolerate a single highest dose of at least 300 mg (443 mg cumulative) of peanut protein with no more than mild symptoms at Exit DBPCFC will be tested with a Type I error rate of 0.05; if this test is significant, then the proportion of subjects who tolerate a single highest dose of at least 1000 mg (2043 mg cumulative) of peanut protein with no more than mild symptoms at Exit DBPCFC will be tested with a Type I error rate of 0.05; if this test is significant, then the proportion of subjects who tolerate a single highest dose of at least 1000 mg (2043 mg cumulative) of peanut protein with no more than mild symptoms at Exit DBPCFC will be tested with a Type 1 error rate of 0.05; if this test is significant, then the maximum severity of symptoms occurring at any challenge dose of peanut protein during the Exit DBPCFC will be tested with a Type I error rate of 0.05. This closed testing procedure maintains the overall Type I error rate at 0.05 (EMEA CPMP, 2002; Cook et al., 2008).

Europe:

- The proportion of subjects aged 4 to 17 years who tolerate a single highest dose of at least 600 mg (1043 mg cumulative) of peanut protein with no more than mild symptoms at the Exit DBPCFC: The statistical analysis to be conducted for this key secondary endpoint will be similar to that used for the primary endpoint.
- The proportion of subjects aged 4 to 17 years who tolerate a single highest dose of at least 300 mg (443 mg cumulative) of peanut protein with no more than mild symptoms at the Exit DBPCFC: The statistical analysis to be conducted for this key secondary endpoint will be similar to that used for the primary endpoint.

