# **1.1. DOCUMENT HISTORY**

SAP Final Version 1 was approved prior to the first ARC003 subject unblinding (Dec2016). Updates for Version 2 of the SAP are being made post-unblinding of several subjects. It is important to note that all Aimmune and Agility Clinical, Inc. (Agility) staff involved in SAP development and study conduct responsibilities remain blinded to subjects' treatment assignments. The staff will remain blinded until the full study is unblinded post database lock.

Version 2 of the SAP incorporates feedback received by Aimmune from regulatory authorities on the ARC003 study protocol. The FDA correspondence was dated 13Jan2017 and notes the FDA's concern about the number of adult subjects in the study. Per the FDA, licensure of AR101 will likely be possible only in pediatric subjects ages 4-17 years. As such, the efficacy and safety endpoints have been modified in this version of the SAP and in the study protocol to note the primary population for analysis of all endpoints is in the pediatric population. The definition of EU primary and secondary endpoints were integrated in this SAP.

Other notable changes from Version 1 to Version 2 of the SAP include:

- The proportion of subjects aged 18 to 55 years who tolerate a single highest dose of at least 600 mg (for North America) and of at least 1000 mg (for EU) of peanut protein with no more than mild symptoms at the Exit DBPCFC was added as a key secondary efficacy endpoint.
- A tipping point sensitivity analysis of the primary efficiacy endpoint was added based on FDA feedback.
- The mITT population was removed as an analysis population since it was decided that sufficient sensistivity analyses of efficacy endpoints are defined in the SAP without including an mITT population.
- An SMQ search analysis of hypersensitivity events occurring with 2 hours of each other will be presented.
- Adverse event summaries combining adverse events collected on the adverse event page with including in-clinic dosing symptoms will be presented

Other changes have been made but do not materially alter analytical methods or planned summaries detailed in Final Version 1 of the SAP (dated 07Dec2016).

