#### **3.2. SECONDARY ENDPOINTS**

#### 3.2.1. Key Secondary Efficacy Endpoints

North America: The hierarchal order of key secondary efficacy endpoints is as follows:

- 1. The proportion of subjects ages 4-17 who tolerate a single highest dose of at least 300 mg (443 mg cumulative) of peanut protein with no more than mild symptoms at the Exit DBPCFC
- 2. The proportion of subjects ages 4-17 who tolerate a single highest dose of at least 1000 mg (2043 mg cumulative) of peanut protein with no more than mild symptoms at the Exit DBPCFC
- 3. The maximum severity of symptoms in subjects ages 4-17 occurring at any challenge dose of peanut protein during the Exit DBPCFC
- 4. The proportion of subjects aged 18 to 55 years who tolerate a single highest dose of at least 600 mg (1043 mg cumulative) of peanut protein with no more than mild symptoms at the Exit DBPCFC

Europe: The hierarchal order of key secondary efficacy endpoints is as follows:

- 1. The proportion of subjects ages 4-17 who tolerate a single highest dose of at least 600 mg (1043 mg cumulative) of peanut protein with no more than mild symptoms at the Exit DBPCFC
- 2. The proportion of subjects ages 4-17 who tolerate a single highest dose of at least 300 mg (443 mg cumulative) of peanut protein with no more than mild symptoms at the Exit DBPCFC
- 3. The maximum severity of symptoms in subjects ages 4-17 occurring at any challenge dose of peanut protein during the Exit DBPCFC

4. The proportion of subjects aged 18 to 55 years who tolerate a single highest dose of at least 1000 mg (2043 mg cumulative) of peanut protein with no more than mild symptoms at the Exit DBPCFC

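### SAP 9.5 and SAP 9.3 disagree on whether the adult test must succeed before the other secondary endpoints are tested; read literally, 9.5 allows a familywise error of up to 9.75%

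*SAP*

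**What the plan says.** SAP 3.2.1 lists as the fourth key secondary for North America "The proportion of subjects aged 18 to 55 years who tolerate a single highest dose of at least 600 mg"; the European list has the adult step at 1000 mg in the same position. SAP 1.1 records that this endpoint "was added as a key secondary efficacy endpoint" in Version 2. SAP 9.3 keeps that order and evaluates each comparison "only if all of the preceding tests in the hierarchy and the primary analysis of the primary endpoint are statistically significant in favor of AR101". It then states an overall Type I error of 0.05, as Protocol 9.2.2.1 does: "This closed testing procedure maintains the overall Type I error rate at 0.05".

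SAP 9.5 sets the condition for going further: the primary analysis and "all of the hierarchical testing of key efficacy secondary endpoints in pediatric subjects" must be significant. The same sentence refers back to Section 9.3 and says testing goes on "according to the same hierarchical closed testing procedure used for the key efficacy secondary endpoints". A later paragraph adds: "The other secondary endpoints are included in the overall hierarchical testing procedure". It also calls these endpoints supportive and rules out labeling claims on them. SAP 6.3 provides no other multiplicity adjustment.

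Protocol 9.2.2.1 orders the key secondaries by Section 3.7.1, which has the adult endpoint fourth in both regions. Its step-by-step text, however, ends at maximum symptom severity. Protocol 9.2.2.2 gives no entry rule for the other secondaries.

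**The concern.** A fixed sequence at full alpha controls familywise error because testing ends at the first failure. The entry condition in SAP 9.5 names only pediatric key secondaries, and step 4 is the one key secondary that contains no children. Taken at its word, the condition is met after step 3 whatever happens in adults. The sequence then forks into the adult test and the chain of other secondaries, each at 0.05, with no adjustment for the fork.

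What is at stake is the status of the other secondary p-values if the adult test fails: confirmatory under one reading, nominal under the other. The documents leave that to be decided after the results are known.

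**Working it through.** **1. The plan's own figure.** Each test is two-sided at 0.05 (SAP 6.4). In the worst case for a fixed sequence, every null before the first true one is false and is rejected. The error is then that of the first true null alone: 1 − (1 − 0.05) = 0.05. This matches the stated rate, and it applies to the whole chain if the adult step must succeed.

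**2. Literal reading of 9.5.** After step 3, the adult test and the first true null among the other secondaries are both tested at 0.05. Adults and children are different subjects, so the two tests are independent:

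- two-sided: 1 − 0.95² = 1 − 0.9025 = 0.0975
- false wins in favour of AR101 only: 1 − 0.975² = 1 − 0.950625 = 0.0494, against 0.025

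A simulation of 2,000,000 trials gave 0.0974 with one true-null other secondary and 0.0977 with six (correlation 0.5). With the adult step required it gave 0.0499 in both cases. The bound does not grow with the number of other secondaries, because they stay sequential among themselves.

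**3. Scope.** The primary and the four key secondaries form a single chain under either reading, so their familywise error is 0.05 both ways.

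**4. How often the readings would part.** They differ only when steps 1 to 3 succeed and the adult step fails.

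- Adults from SAP 2.4: 555 − 499 = 56, about 42:14 at 3:1.
- Adults from Protocol 9.4: 554 − 495 = 59, about 44:15.
- Test: Farrington-Manning against 0, two-sided 0.05 (SAP 9.3.1).
- Rates: the planning rates for the pediatric analysis, applied to adults as an assumption. For Europe, 44% is also shown because SAP 2.4 and Protocol 9.4 report it for AR101 from the earlier studies.

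Power = Φ[(p₁ − p₀ − δ − 1.96·SE₀)/SE₁], with SE₀ at the null-restricted rates and SE₁ at the assumed rates. The method reproduces the plan. With 371:124 children it gives 88.9% for 50% vs 20% at margin 0.15 (stated: 89%), and 93.5% for 30% vs 15% against 0 (stated: at least 93%).

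Adults, 50% vs 20%, 42:14:

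- pooled rate (21 + 2.8)/56 = 0.425
- SE₀ = √[0.425 × 0.575 × (1/42 + 1/14)] = 0.1526
- SE₁ = √(0.25/42 + 0.16/14) = 0.1318
- power = Φ[(0.30 − 0.2990)/0.1318] = 50.3%

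| Adult step | 42:14, formula / exact | 44:15, formula / exact |
|---|---|---|
| North America, 50% vs 20% | 50.3% / 52.5% | 53.2% / 55.0% |
| Europe, 30% vs 15% | 16.4% / 16.1% | 17.5% / 16.7% |
| Europe, 44% vs 15% | – / 51.2% | – / 53.8% |

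Exact means full binomial enumeration of the same test.

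**The case against.** The strongest reply is that the strict rule is already in the text. SAP 9.5 points back to 9.3, carries on the same closed procedure and places these endpoints in one overall hierarchy. In 9.3 the adult test is a preceding step, so its failure stops everything after it. The SAP also uses the word pediatric loosely: 9.3 describes its hierarchical analysis population as pediatric just after listing an adult test, and 9.3.1 does the same although it is the only method given for that test. The restriction in 9.5 may be left over from before the adult endpoint was added in Version 2, though that is an inference. This reply stands far enough that the literal reading cannot be called the plan's settled rule. It does not remove the conflict, because nothing says which sentence prevails.

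A second reply concerns size. The first two other secondaries, maximum tolerated dose and its change from baseline, come from the same pediatric Exit DBPCFC as the response rates. If the response differences are real, nulls there are implausible, so a true null would have to sit further down, for example at quality of life. That is right. The 9.75% is therefore a ceiling, and any chance of failure before that point lowers it.

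A third reply is that little depends on these endpoints, since the SAP disclaims labeling claims on them. That limits the seriousness, but 9.5 still places them under error control.

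**Conclusion.** SAP 9.3 and 9.5 conflict on the role of the adult step. Under the stricter reading the familywise error is 5%. Under the literal reading it is at most 9.75% two-sided, or 4.9% instead of 2.5% in favour of AR101, over the primary, key and other secondaries. Reaching that ceiling requires a true adult null, at least one true null among the other secondaries, and all earlier nulls false and rejected.

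Two stronger conclusions are tempting and are not supported:

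- **That the stated 5% is broken.** The sentences claiming it in SAP 9.3 and Protocol 9.2.2.1 close the key-secondary procedure, and that procedure holds under both readings. The protocol places no other secondary endpoint in a hierarchy.
- **That low adult power measures the inflation.** The power figures assume the adult null is false; the 9.75% needs it true. If adults do benefit, the error over the rest of the chain is 5%.

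The power figures show only that the ambiguity is likely to matter. If the planning rates carry over to adults, the adult step fails in roughly half of trials for North America (power 50–55%). For Europe, power runs from about 16–18% at 30% vs 15% to about 51–54% at 44% vs 15%.

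**What to change.** Before database lock, settle the rule in SAP 9.5 in one of two ways:

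- delete the pediatric qualifier from the entry condition, so that all four key secondaries must succeed; or
- state that the other secondaries are descriptive and outside the hierarchy.

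In either case, add the adult step to the written-out sequences in Protocol 9.2.2.1 for both regions, to match Section 3.7.1.

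If the other secondaries stay in the hierarchy, name one test per step. Epinephrine use has a Fisher test for each challenge type (SAP 9.5.3). The immunoglobulin step has IgE, IgG4 and their ratio (9.5.4). Quality of life has two instruments, summarised separately by age group and respondent (9.5.6). SAP 9.5.3 also makes the Completer analysis primary for epinephrine, while 9.5 excludes Completer analyses from the hierarchy; these need reconciling.

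The cost is wording only. The downside of the first option is that supportive pediatric p-values will depend on a small adult group and become nominal more often. As no labeling claim rests on them, that is a modest price for a rule fixed in advance.
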